
Objectives

The purpose of this study is to assess the efficacy of intraoperative intravenous nonsteroidal antiinflammatory drug (ketorolac) versus intravenous (dexamethasone) administration on dysphagia and dysphonia after ACDF. Primary measures for dysphagia include the classification of the Bazaz and EAT-10 outcome results. The primary measures for Dysphonia will be analyzed by the Voice Handicap Index (VHI-10). Secondary measurements include result classification utilizing results from the Neck Disability Index(NDI) and Visual Analogue Pain Scale (VAS) for neck pain. Additional measurements to be analyzed are comparisons in complication factors in surgical site infection, need for re-operation and pseudoarthrosis.

Design

An on-line randomization generator will be used www.researchrandomizer.org.

Randomization will be an equal split between the three groups with no predictable pattern. The subject has a one in three chance of being randomized to any of the three different groups.

Subjects are blinded to the randomization assignment. This is a single blinded study. The treating physician and study personnel will know which group the subject is randomized into.

The lead study coordinator will track the randomization assignments, withdrawals and study completions. Once 25 from each of the 3 groups have completed the study, the study will cease enrollment.

Methods

Each study participant will have equal chance of being assigned to one of the three study groups. The subjects medical record will be reviewed and the data collected/documented will include: gender, age, diagnosis or reason for surgery, co-morbidities, medications, BMI pre-operative and post-operatively. All clinic follow-up progress notes will be reviewed to specifically collect any findings documented as complications from surgery.

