Subjects who elect to consent into the study will be assigned a random study number and randomized into three cohorts: control (no steroid or NSAID), IV NSAID (1-time dose of 30 mg of IV ketorolac at the time of closure), and IV steroid (1-time dose of 10 mg of IV dexamethasone at the time of closure). Randomization schedule will be performed in a 1:1:1 fashion. Patients will be blinded with regard to which treatment they received until at least 1 year after surgery. Those subjects whom willingly volunteer to be part of the study will be notified promptly if they are found to not meet trial criteria and advised that they will be automatically withdrawn from the study.

Patient outcomes (patient completed questionnaires to evaluate for dysphagia and dysphonia) will be collected preoperatively and at 1 day (post-surgical day to day 3 post-op), 3 weeks (+/- one week), 6 weeks (+/- two weeks), 3 months (+/- three weeks), 6 months (+/- one month), and 1 year (+/- three months) postoperatively and will include: The Eating Assessment Tool (EAT-10), The Voice Handicap Index (VHI-10), Neck Disability Index (NDI), and Visual Analogue Pain Scale (VAS), Bazaz classification for dysphagia.

Post operative questionnaire collection will occur at time of outpatient clinic follow-up or subject may be called by phone and data collected over the phone or questionnaires mailed if patient preference. (Clinic visit follow up per the usual standard of medical care is per the above data collection timeline points, however, many times patients are feeling better and do not return for all suggested follow-up).

Eligibility

Inclusion

>/= 19 years of age Undergoing ACDF for radiculopathy or myelopathy No known allergies or sensitivities to steroid or non-steroidal medications This is not an ACDF revision procedure or surgery related to treatment of trauma, infection or tumor.

Exclusion

Procedure is being done for revision, trauma, infection or tumor. Patients with known diagnosed metabolic diseases (diabetes, pancreatitis, gout, electrolyte imbalances, hypertension, hematological abnormalities including gastrointestinal bleeding...) Patients with known kidney disease or a creatinine level above the upper limit of normal > 1.27) (BMet labs are completed pre-operatively as standard of care on all patients unless there is documentation of normal labs completed within the past 6 months of surgery).

Patients with known allergy or sensitivities to steroid or non-steroidal medications

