
Statistical Analysis Plan

For dysphagia, primary outcome measures will be the Bazaz classification and the EAT-10. For dysphonia, primary outcomes will be measured by the VHI-10. Secondary outcomes will be measured with Neck Disability Index (NDI), Visual Analogue Pain Scale (VAS) for neck pain. Complications will also be documented for comparison to include: surgical site infection, need for reoperation and pseudoarthrosis.

Descriptive statistics (specifically counts and percentages) will be computed for all variables to ensure data quality and to evaluate the assumptions of statistical tests. Fisher's exact test will be used to evaluate associations between treatment groups and categorical measures at each time point. Analysis of variance (ANOVA) or the Kruskal-Wallis test, depending on the distribution of the data, will be utilized to compare continuous variables between the groups. If the overall p-value from ANOVA is statistically significant, pairwise comparisons will be performed and adjusted using Tukey's method. Mixed effect models also will be explored, with time, treatment group, and time x treatment group interaction terms as fixed effects and with a random intercept term to account for repeated measures All tests will be 2-sided and a p-value < 0.05 will be considered statistically significant.

No analysis was ultimately completed due to poor follow-up and lack of data.

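### On the ANOVA route the SAP stacks an F-test condition on Tukey's adjustment, although with three arms either one alone holds the family-wise error at 5%

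*Combined protocol and SAP*

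**What the plan says.** The Objectives section gives the purpose as to "assess the efficacy of intraoperative intravenous nonsteroidal antiinflammatory drug (ketorolac) versus intravenous (dexamethasone) administration on dysphagia and dysphonia after ACDF". The Methods section randomises equally to three arms: control, ketorolac and dexamethasone. The Design section sets the size by a stopping count: "Once 25 from each of the 3 groups have completed the study, the study will cease enrollment".

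For continuous measures the Statistical Analysis Plan says: "Analysis of variance (ANOVA) or the Kruskal-Wallis test, depending on the distribution of the data, will be utilized to compare continuous variables between the groups". The pairwise rule follows: "If the overall p-value from ANOVA is statistically significant, pairwise comparisons will be performed and adjusted using Tukey's method". The level is set by: "All tests will be 2-sided and a p-value < 0.05 will be considered statistically significant". The SAP names no primary contrast and exempts no pair from the F condition or from the adjustment. It gives no pairwise procedure after Kruskal-Wallis, sends categorical measures to Fisher's exact test, and offers mixed models only as exploration.

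**The concern.** The drug-versus-drug comparison stated as the purpose must pass a three-group F test and must then pass a critical value set for three pairs. Each step is a complete multiplicity control for a three-arm comparison. Applying both pushes the error rate below the nominal 5% and gives up power for no added protection. With 25 completers per arm there is little power to spare, and the Methods section itself expects incomplete attendance: "many times patients are feeling better and do not return for all suggested follow-up".

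**Working it through.** **Inputs from the documents.** Two-sided 0.05 (SAP); three arms with 25 completers each (Design); equal allocation (Methods: "Randomization schedule will be performed in a 1:1:1 fashion"). Error df = 75 − 3 = 72.

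**Inputs not in the documents.** The SD, effect size d (in SD units), target power and position of the control mean are assumed. I varied d from 0.3 to 1.2. The control mean was placed midway between the drugs, equal to one drug, 0.5 SD worse than the worse drug, or d worse than it. Normal data with a common variance are assumed. The plan has no power figure to reproduce.

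**Critical values.**
- Unadjusted pair: t(0.975; 72) = 1.993.
- Tukey pair: q(0.95; 3, 72)/√2 = 3.384/1.414 = 2.393, a per-pair level of 0.0193.
- F test: F(0.95; 2, 72) = 3.124.

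**Why one layer is enough.** Tukey's method controls all three pairs by construction. For the F test with unadjusted pairs there are three cases:
- All three means are equal: any false rejection needs a significant F test, which has probability 5%.
- Exactly two means are equal: only one pair can be falsely rejected, and it is tested at 5%.
- All means differ: no pair can be falsely rejected.

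This argument fails with four or more arms.

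**Error rates by simulation (1,000,000 trials, all means equal).**

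| Rule | Family-wise error |
|---|---|
| Tukey alone | 5.0% |
| F test, then unadjusted pairs | 5.0% |
| F test, then Tukey (as written) | 4.5% |

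Under the written rule each single pair is rejected 1.8% of the time. With the drugs equal and control 0.8 or 2 SD away, the F test with unadjusted pairs rejects the drug pair 4.9% to 5.0% of the time.

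**Power for ketorolac versus dexamethasone, assumed d = 0.8.** The noncentrality is 0.8/√(2/25) = 0.8/0.283 = 2.83 on 72 df. The noncentral t gives 79.7% at 1.993 (one planned contrast) and 66.8% at 2.393 (Tukey alone). The joint rules were simulated.

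| Control mean | As written | Tukey alone | F, then unadjusted | Planned contrast |
|---|---|---|---|---|
| Midway | 65.4% | 66.8% | 68.7% | 79.7% |
| Equal to one drug | 66.4% | 66.8% | 75.1% | 79.7% |
| 0.5 SD worse than both | 66.8% | 66.8% | 79.6% | 79.7% |
| 0.8 SD worse than both | 66.8% | 66.8% | 79.7% | 79.7% |

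**Splitting the cost at d = 0.8.**
- F condition added to Tukey: 66.8 − 65.4 = 1.4 points at most, and 0.0 at least.
- Tukey added to the F condition: 68.7 − 65.4 = 3.3 points (control midway) up to 79.7 − 66.8 = 12.9 (control well away).
- Whole rule against one planned contrast: 79.7 − 66.8 = 12.9 up to 79.7 − 65.4 = 14.3. Tukey alone accounts for 12.9 of these.

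**Loss against one planned contrast at other assumed effects (points).**

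| d | 0.3 | 0.4 | 0.5 | 0.6 | 0.7 | 0.8 | 0.9 | 1.0 | 1.2 |
|---|---|---|---|---|---|---|---|---|---|
| Loss | 8.4–9.0 | 11.6–12.5 | 14.2–15.4 | 15.5–16.9 | 15.0–16.5 | 12.9–14.3 | 9.7–10.9 | 6.7–7.5 | 2.1–2.5 |

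The F condition's own share on top of Tukey never exceeds about 1.5 points at any d tried.

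**The case against.** A reader might infer that paying for multiplicity twice costs 13 to 14 points. The figures do not support that. The comparator behind that number is a single contrast that pays nothing for multiplicity, and nearly all of the gap is ordinary three-pair Tukey. This part of the objection stands in full. It also means that deleting only the F condition is tidying and recovers almost no power.

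A reader might also infer that drug versus drug is the trial's only question. The Objectives sentence leans that way. But a third of patients go to a control arm, the Background describes both steroid and no-steroid practice as standard care, and the SAP designates no contrast. All-pairs testing is a reasonable choice for such a design, so demoting the control comparisons is a choice of hierarchy rather than the correction of an error.

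The scope is narrow. The rule does not touch Kruskal-Wallis or Fisher analyses, and Bazaz would fall under Fisher if treated as categorical. Multiplicity across outcomes and visits is untouched. EAT-10 and VHI-10 at six postoperative visits could give 12 drug-pair tests. If they were independent and all null, the chance of at least one false positive would be 1 − 0.982^12 = 20% at the written 1.8% level and 1 − 0.95^12 = 46% at 5%; correlation would lower both. A planned contrast at 5% therefore needs one primary outcome and visit first.

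Finally, the rule is conservative, and the SAP closes by reporting that no analysis was completed, so no result was affected. None of this removes the redundancy, which can be corrected at no cost to the 5% level within an outcome and visit.

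**Conclusion.** The point holds as a redundancy on the ANOVA route, within each outcome and visit. The written rule is valid but stricter than it needs to be. How much power the second layer costs depends on which layer is treated as surplus: very little if it is the F condition, and a moderate to substantial amount if it is Tukey, with the control mean's position deciding where in that range it falls. The larger loss, about 2 to 17 points over assumed effects of 0.3 to 1.2 SD, is the price of designating no single primary contrast and should not be charged to the double layer.

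All power figures rest on assumed effects, normal data with equal variances, and 25 completers per arm at the visit analysed. Poorer attendance would change them. The point matters for any reuse of this plan and says nothing about a reported finding.

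**What to change.** In the Statistical Analysis Plan, replace the pairwise sentence so that only one layer remains. The preferred form is: after a significant three-group F test at 0.05, test the three pairs with unadjusted two-sided t tests using the pooled error term. State that this is valid because there are exactly three arms. Tukey's method without the F condition is equally valid but gains at most about 1.5 points over the present rule. Either form costs one sentence, needs no extra patients, and keeps the 5% family-wise level within an outcome and visit.

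Optionally, in line with the Objectives and only after naming a single primary outcome and visit, prespecify ketorolac minus dexamethasone as the primary contrast. Test it at two-sided 0.05 with the pooled error term whatever the F result, and make the two control contrasts secondary. This recovers the full loss. Its cost is that the control contrasts leave the primary error family, so the sponsor should decide it explicitly.

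### The SAP has no missing-data method, its committed tests use only patients with data at each visit, and the protocol expects patients who feel better to miss visits

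*Combined protocol and SAP*

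**What the plan says.** The Statistical Analysis Plan is short. For dysphagia, "primary outcome measures will be the Bazaz classification and the EAT-10"; for dysphonia, the primary measure is the VHI-10. The committed tests are:

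- **Categorical measures:** Fisher's "exact test will be used to evaluate associations between treatment groups and categorical measures at each time point".
- **Continuous measures:** ANOVA "or the Kruskal-Wallis test, depending on the distribution of the data, will be utilized to compare continuous variables between the groups". After a significant ANOVA, "pairwise comparisons will be performed and adjusted using" Tukey's method.

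A longitudinal model is mentioned but not committed: "Mixed effect models also will be explored", with time, treatment group and their interaction as fixed effects and "with a random intercept term to account for repeated measures". No residual covariance structure, analysis population, missing-data method or sensitivity analysis is named.

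The protocol's Methods section schedules one pre-operative and six post-operative assessments (1 day, 3 weeks, 6 weeks, 3 months, 6 months, 1 year). It remarks that "many times patients are feeling better and do not return for all suggested follow-up" and allows questionnaires by telephone or post. Under Design, enrolment stops at 25 completers in each of three groups. The SAP ends: "No analysis was ultimately completed due to poor follow-up and lack of data".

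**The concern.** A test run visit by visit compares whoever supplied a score at that visit. The protocol itself expects absence to be related to how patients feel. If a drug reduces dysphagia and patients with fewer symptoms are less likely to be assessed, the treated arm loses more of its good scores than the control arm, and the observed difference shrinks. If early benefit drives later absence, a true null at 1 year can look like harm. Enrolling until 25 per group complete fixes a count; it does not remove selection.

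The mixed model is the natural remedy. Fitted by likelihood, it uses every available visit and is implicitly a missing-at-random method. But it is only exploratory, and a random intercept with default residuals is a restrictive description of scores collected from 1 day to 1 year. Simply promoting it as written could introduce a different error.

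**Working it through.** **The plan's own figure.** The documents give 25 completers per group with no effect size, SD, power or dropout rate, so the figure cannot be reproduced. The point does not depend on it.

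**Step 1: which tests are per visit.** Fisher's test is explicitly per time point. For ANOVA and Kruskal-Wallis this is inferred: each takes one value per patient, and no other summary is specified. Use of observed scores only is the default of these tests, not a sentence in the SAP.

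**Step 2: what the random intercept implies.** With independent, constant-variance residuals (the usual default; the SAP names none):

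- Var(Y at any visit) = s_b² + s_e²
- Corr(any two visits) = s_b² / (s_b² + s_e²)

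With s_b² = 0.6 and s_e² = 0.4, the variance is 1.0 at all six visits and every correlation is 0.6. To see the consequence with complete data, suppose the true SDs fall 10, 9, 8, 7, 6, 5. The mean variance is (100+81+64+49+36+25)/6 = 59.17. The nominal 5% test then has true size 2×(1 − Φ(1.96×√(mean variance / visit variance))):

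- Day 1: 1.96×√(59.17/100) = 1.51, size about 13%
- 1 year: 1.96×√(59.17/25) = 3.01, size about 0.3%

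With equal SDs it is 5% at both.

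**Step 3: size of the respondent-only error.** Every input here is assumed. Control means are 14, 12, 9, 7, 6, 5 over the six visits and effects -4, -4, -4, -3, -2.5, -2. SDs are all 7 or fall from 10 to 5. Correlation is constant at 0.6 or 0.8 per visit step. Return is 87% or 75% per step, with log-odds of return +0.5, +1 or -1 per SD worse score. Loss is the share of the true effect missing from the respondent-only difference in large samples.

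| Situation | Seen at 1 year | Effect lost |
|---|---|---|
| 1 year, visits skipped intermittently | 64-88% | roughly 0-16% |
| 1 year, every missed visit permanent | about 15-60% | 8-50% |
| 3 weeks | not applicable | about 2-16% |
| 1 year, permanent, return driven by a symptom correlated 0.3 with the score | not given | 0-8% |
| Neither drug has any effect | any | none in the difference |

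In points at 1 year: 0.16×2 = 0.32 at most with intermittent absence; 0.08×2 = 0.16 to 0.50×2 = 1.0 with permanent dropout. With permanent dropout driven by the last score and a true 1-year effect of 0 after early effects, respondents show +0.4 to +1.0.

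**Step 4: would a longitudinal model help?** Under permanent dropout with a true effect of -2:

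- *Return depends on the last score:* an unstructured model gives about -2.0. The random intercept gives -2.0 if SDs and correlations are equal, otherwise -2.07 to -2.74.
- *Return depends on the current score:* respondents give -1.81 to -1.06 and the unstructured model -1.94 to -1.56, so (2−1.94)/2 = 3% to (2−1.56)/2 = 22% is still lost.

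**Step 5: against sampling error.** With 25 per arm and SD 7, SE = 7×√(2/25) = 1.98 points. The difference detectable with 80% power (two-sided 0.05, unadjusted pairwise) is 0.79 SD, or 0.79×7 = 5.5 points. The largest loss in Step 3, about 1.0 point, is about half of one SE.

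**The case against.** The strongest objection is that the size is a product of assumptions the documents do not supply. This stands in four respects.

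- **Pattern.** The Methods remark describes patients who do not attend every visit, which fits skipped visits at least as well as permanent loss. Intermittent absence brings the 1-year loss down to roughly 0-16%. Poor follow-up could still mean heavy loss, but no rate is given.
- **Which symptoms.** Surgery is for radiculopathy or myelopathy, and the remark does not say what has improved. If it is neck or arm symptoms only weakly related to swallowing, the bias is smaller still.
- **Visit.** No primary visit is named, and 1 year is where selection accumulates most.
- **Precision.** A 2-point effect would be largely undetectable by either method at this sample size.

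Two further defences are weaker. Telephone and postal collection is a real mitigation, but follow-up was still reported as poor. A mixed model is in the plan, and in the assumed settings even the random intercept was closer to the truth than respondents in 57 of 64; but it is not committed, and it can overstate a late effect.

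A reader might infer that half of any treatment effect would have been lost, or that the failed follow-up shows that well patients stayed away. The documents support neither: the upper figure needs permanent dropout at the last visit, and the SAP does not say who was missing or why. Nor do they show that equal variance and correlation were definitely imposed, since no residual structure is stated.

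**Conclusion.** The gap is real. The protocol anticipates outcome-related absence, and the SAP commits only to tests that ignore it. The direction of error follows if a drug works and return depends on swallowing or voice symptoms. The error is systematic, so more enrolment would not remove it, but under the assumptions examined it is smaller than the sampling error of a trial with 25 per arm. If neither drug has any effect, the between-arm difference is unbiased, although respondent-only rates of dysphagia could still be wrong. The criticism of the random intercept is conditional on default residuals.

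Severity is minor for this trial, because no analysis was run and no reported result is affected. The point matters for the plan as written, for any post hoc use of the scores, and for reuse of the plan elsewhere.

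**What to change.** (a) For EAT-10 and VHI-10, make the primary analysis a likelihood-based repeated-measures model on all randomised patients with any post-operative score. Include arm, visit, arm × visit and pre-operative score × visit, with estimates at each visit and Tukey-adjusted pairwise comparisons. Keep per-visit ANOVA or Kruskal-Wallis as sensitivity analyses. This does not settle which visit is primary, or multiplicity across visits and outcomes.

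(b) Use an unstructured covariance (6×7/2 = 21 parameters) with a small-sample correction such as Kenward-Roger. If it does not converge, use heterogeneous Toeplitz (6+5 = 11), then heterogeneous AR(1) (6+1 = 7), and state which was used.

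(c) Add one delta-adjustment analysis for absence that depends on current symptoms: shift missing scores in one arm at a time over a stated range and report where the conclusion changes. A range of -4 to +4 points would cover the -3.5 to +3.6 needed in the assumed settings; widen it if observed SDs are larger.

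(d) For Bazaz, keep Fisher's test at each visit and report numbers missing by arm and visit. If a longitudinal model is added, use a likelihood-based ordinal mixed model as supportive and state its correlation assumption.

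(e) For this trial, label any such analysis post hoc. Report existing scores and complications descriptively by arm with numbers missing. Complications are taken from clinic notes, so they also depend on return.

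The cost is SAP wording and standard model fits, with no new data; under Design, a coordinator already tracks withdrawals and completions. The downside is more covariance parameters with few patients. In simulation with 25 per arm seen at 1 year, the corrected test had 5.5% type I error. With about 5 per arm it had 8%, and 133/1,500 = 9% of fits failed, so at that level of follow-up only description is dependable.

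### Three primary outcomes at six visits, each test judged at p < 0.05, with no primary visit and no control of error across outcomes or visits

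*Combined protocol and SAP*

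**What the plan says.** The Statistical Analysis Plan sets out the primary outcomes for dysphagia and dysphonia in turn: "primary outcome measures will be the Bazaz classification and the EAT-10. For dysphonia, primary outcomes will be measured by the VHI-10". The Objectives section agrees. The Methods section schedules these questionnaires before surgery and at six postoperative times: 1 day, 3 weeks, 6 weeks, 3 months, 6 months and 1 year. Neither section makes one of these the primary time.

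The tests are described as follows.

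- Categorical measures: Fisher's exact test, "to evaluate associations between treatment groups and categorical measures at each time point". Bazaz is a classification, so this covers one primary outcome explicitly.
- Continuous measures: ANOVA or Kruskal-Wallis, which "will be utilized to compare continuous variables between the groups". No visit is mentioned.
- Pairs of arms: "If the overall p-value from ANOVA is statistically significant, pairwise comparisons will be performed and adjusted" by Tukey's method.
- Repeated measures: "Mixed effect models also will be explored", with time, arm and their interaction, but no term is designated as the primary test.

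The decision rule for all of this is "All tests will be 2-sided and a p-value < 0.05 will be considered statistically significant". The section closes with "No analysis was ultimately completed due to poor follow-up and lack of data".

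**The concern.** Two clinical questions are to be answered with three scales, up to six visits per scale, and a 5% threshold on each test. The plan does not say which result, or how many, would count as showing a treatment effect. A single significant result on one scale at one visit could therefore be presented as a primary finding.

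Tukey's adjustment does not help here. It deals with which arms differ once an ANOVA is significant, not with how many ANOVAs or Fisher tests were run. The mixed model could have replaced visit-by-visit testing with one test per scale, but it is only exploratory.

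The text does not settle whether EAT-10 and VHI-10 are tested once or at each visit. If once, the visit is still unnamed and could be chosen after the results are seen.

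**Working it through.** The documents state no familywise error rate, power, effect size or standard deviation, so there is no figure of theirs to reproduce.

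**Inputs from the documents.** Threshold 0.05, two-sided, for all tests; three primary scales (Statistical Analysis Plan). Six postoperative visits (Methods). Three arms, enrolment ending when 25 per arm have completed (Design). Dysphagia prevalence 3% to 67% (Background & Rationale).

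**Assumptions.** Full data; no treatment effect; multivariate normal scores; between-visit and between-scale correlations each 0.3 to 0.7, with 0.9 between visits as a sensitivity. Two scores that differ in both scale and visit take the product of the two correlations.

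**Number of tests if every scale is tested at every visit.** Dysphagia 2 × 6 = 12; dysphonia 1 × 6 = 6; pooled 3 × 6 = 18.

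**Independence reference.** P(at least one p < 0.05) = 1 − 0.95^k:

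- k = 6: 26.5%
- k = 12: 46.0%
- k = 18: 60.3%

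**Correlated tests.** Null simulation with 3 × 25 patients and a one-way F test for each scale and visit, on 2 and 3 × 25 − 3 = 72 degrees of freedom. There were 40,000 trials per setting; repeat runs may differ by about 1 point. The three figures in a cell are for between-scale correlation 0.3 / 0.5 / 0.7.

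| Between-visit correlation | Dysphonia, 6 tests | Dysphagia, 12 tests | Pooled, 18 tests |
|---|---|---|---|
| 0.3 | 24-25% | 42.2 / 40.9 / 37.9% | 55.2 / 52.4 / 47.3% |
| 0.5 | 21-22% | 37.5 / 35.8 / 33.1% | 49.9 / 46.5 / 41.5% |
| 0.7 | 17% | 30.3 / 29.0 / 27.1% | 41.4 / 38.3 / 34.3% |
| 0.9 | 11% | 20.5 / 20.2 / 18.2% | 28.5 / 27.0 / 23.3% |

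Each single test rejected about 5% of the time, as it should. The pooled column applies only if the two questions are treated as one family.

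**Other correlation structures.** With one common correlation of 0.7 to 0.3 among all tests, the 12 dysphagia tests give about 24-40% and the 18 pooled tests 29-52%. If correlation decays with distance between visits, the six VHI-10 tests give 20-25%.

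**Fisher's test for Bazaz.** Fisher's exact test is conservative. For a yes/no outcome at 25 per arm, its exact size is 0.5% at 3% prevalence, 3.0% at 10%, 3.8% at 15% and 4.3-4.4% at 30-67%. With Bazaz taken as yes/no (an assumption) and F tests for EAT-10, the 12 dysphagia tests give:

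- 30-41% at constant prevalence of 15% to 67%
- 18-28% at constant prevalence of 3%
- about 25-38% if prevalence falls over the six visits (assumed 60-40-25-15-8-3% and 50-20-10-5-3-3%)

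**Narrowest reading.** Bazaz at six visits, EAT-10 and VHI-10 once each:

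- Dysphagia, 6 + 1 = 7 tests: 1 − 0.95^7 = 30.2% if independent; 20-28% by F test at correlations 0.3-0.7; 14-15% at between-visit correlation 0.9. With Fisher for Bazaz: 21-26% at prevalence 15-67%, 16-23% with falling prevalence, 7-8% at 3%.
- Dysphonia, 1 test: 5%.
- Pooled, 8 tests: 1 − 0.95^8 = 33.7% if independent; 22-32% at correlations 0.3-0.7.

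**The case against.** The strongest objection is that nothing was analysed. No p-value exists to be inflated, and the documents announce neither a later analysis nor reuse of the plan. That stands, and it limits the consequence. It does not repair the rule, which would still govern any analysis done under this plan.

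The second objection concerns the main range. It uses F tests throughout, although Bazaz goes to Fisher's test. The Background also describes most postoperative dysphagia as transient, so later visits would have few events and Fisher would rarely reject. This is fair and lowers the dysphagia figure: to about 25-38% with falling prevalence, and to 18-28% if prevalence is 3% throughout. All of these are well above 5%.

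Third, testing at every visit is written only for categorical measures. This also stands. On the narrow reading dysphonia has no inflation beyond the unnamed visit, and with 3% prevalence throughout dysphagia falls to 7-8%.

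Fourth, full data are assumed although follow-up was poor. With an assumed 15 per arm and falling prevalence, the 12-test figure is 24-36%, so smaller groups change little.

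Finally, dysphagia and dysphonia are separate questions and need not share one error rate. That is a legitimate choice, and it is why the main figures are given for each question. Dysphagia alone still has two primary scales and several visits.

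**Conclusion.** The concern holds. As written, the plan lets any of several primary-outcome tests succeed at 5% with no rule for combining them. If each scale is tested at each visit, the null chance of at least one significant result is about 27-42% for dysphagia and 17-25% for dysphonia, given F tests, 25 per arm, full data and assumed correlations of 0.3-0.7. Higher correlation, rarer Bazaz events or the narrower reading reduces these figures. For dysphagia they stay above 5% in every case examined, the lowest being 7-8%. For dysphonia on the narrow reading, the only defect is that the visit can be picked afterwards.

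This is a fault in the plan and not in any published result. It should be corrected before the collected data are analysed or the plan is used again.

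**What to change.** Amend the Statistical Analysis Plan before any analysis:

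1. For each primary scale, state either one primary visit or one overall repeated-measures treatment test, and name the model term tested. The sponsor should choose the visit and justify it.
2. Apply Holm at an overall 0.05 across the outcomes kept as primary: three if Bazaz stays, two if the sponsor makes it supportive. With three, the ordered p-values are compared with 0.05/3 = 0.0167, 0.05/2 = 0.025 and 0.05, stopping at the first failure. If the sponsor prefers to control error separately for dysphagia and dysphonia, the SAP should say so.
3. Report the other visits as estimates with 95% confidence intervals and make no claim of significance for them.
4. Date the choice and describe it as made after data collection. The Design section says study personnel know the allocation, and the poor follow-up is already known, so it cannot be called pre-specification.

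In simulation at a single visit (between-scale correlation 0 to 0.7), three unadjusted outcomes give 11.1-14.0%, Holm across three gives 3.9-4.8%, and Holm across two gives 4.3-4.9%.

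The cost is SAP wording. The other visits become supportive, Holm takes some power from each outcome, and a late choice carries less weight than one made before the data were collected.
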